3 DECISION RULE FOR DOSE ESCALATION AND SIMULATION

Dose escalation recommendations for BMS-986242 monotherapy and in combination with nivolumab will be based on the inference from the Bayesian posterior and the probability that the true DLT rate for each dose lies in 1 of the following categories:

- [0%, 16%) under-dosing
- [16%, 33%) targeted toxicity
- [33%, 100%] excessive toxicity

These boundaries are similar to the toxicity boundaries used by a rule-based design (ie, 3 + 3 design) in that a minimum is set at 16% (about 1 in 6) DLT rate and a maximum at 33% (about 2 in 6) DLT rate. Following the principle of EWOC, dose recommendations for the next cohort will be based on the Bayesian model after DLT information becomes available during the DLT period, accounting for all of the available data from the administered doses, and the candidate doses are the ones fulfilling the overdose criterion that there is less than 25% (for monotherapy) and 35% (for combination therapy) chances of excessive toxicity. Only the candidate doses will be considered for the next cohort. While the Bayesian model will use DLT information from the DLT period only, clinical assessment will take into consideration of the totality of available data including PK/Pharmacodynamics from all treated participants.

The MTD is the highest administered dose not expected to cause DLT in more than 33% of the treated participants during the DLT period. The final recommended MTD/RP2D will be based on the recommendation from the BLRM/BLRM-copula, and on an overall assessment of all available safety, PK/Pharmacodynamic, and efficacy data.

3.1 Simulation Parameters

One thousand trial simulations were used for each scenario. All simulations were run using EAST 6.3.1[®] software for BLRM model for BMS-986242 monotherapy and in-house developed code via R and Openbugs for BLRM-copula method for BMS-986242 in combination with nivolumab. The number of participants to be treated in each cohort in a specific dose level and the stopping rules used to declare MTD are defined as:

- Fixed cohort size: 3
- Probability of overdosing: < 25% for BLRM and 35% for BLRM-Copula
- Probability of achieving the target toxicity: > 50%
- Maximum number of participants treated: 30
- Minimum number of participants treated at a given dose level in order to declare MTD: 6
- Maximum number of participants at a dose: 12

The provisional dose levels for BMS-986242 monotherapy are 25 mg through 600 mg. For the combination therapy, nivolumab is fixed at 480 mg flat dose for Q4W.

3.2 Operating Characteristics

[Section 3.2.1](#) demonstrates operating characteristics of BLRM for monotherapy and [Section 3.2.2](#) demonstrates operating characteristics of BLRM-copula for combination therapy accounting for joint toxicity of the combination therapy.

3.2.1 Operating Characteristics of BLRM for Monotherapy

Three scenarios were investigated by selecting (1) dose-DLT relationship derived by prior, (2) narrow safety window in order to explore how EWOC limits the risk of exposing participants from a toxic dose level, and (3) all doses above the target toxicity (Table 4).

Table 4: Simulation Results of BLRM for Monotherapy

Scenario	BMS-986242 Dose (mg)	25	50	100	200	400	600	MTD not selected (%)	Fitted MTD	Toxicity Observed (%)	Avg # Pts
By Prior	% DLT	2	4	7	13	22	30				
	% MTD	0	0	2.6	25.9	46.5	24.7	0.2	598.8	17.6	18.4
	# Pts	3.1	0.2	0.8	4.2	6.6	3.5				
	# DLTs	0.0	0.0	0.0	0.1	1.3	1.2				
Narrow Safety Window	% DLT	2	4	7	13	22	60				
	% MTD	0.2	0.3	1.7	29.7	62.9	4.8	0.4	546.6	19.6	18.3
	# Pts	3.1	0.2	0.9	4.7	7.3	2.1				
	# DLTs	0.1	0.0	0.0	0.6	1.6	1.3				
All High	% DLT	40	50	60	70	75	80				
	% MTD	8.8	3.9	1	0.2	0	0	86.1	28.7	54.8	7.7
	# Pts	4.6	1.5	0.7	0.3	0.6	0				
	# DLTs	1.8	0.7	0.4	0.2	0.4	0				

Note: % DLT = true DLT rate; % MTD = proportion of the dose selected as the MTD; # Pts = average number of participants by adjusting for skipped dose level where the true toxicity rate is below the target rate; # DLTs = average number of DLTs by adjusting for skipped dose level where the true toxicity rate is below the target rate; Fitted MTD = fitted MTD at 33% as the target toxicity rate; % toxicity observed = average proportion of DLTs given the doses were tried

Doses with true target toxicity within the target toxicity interval [16%, 33%)

Abbreviations: Pts = participants.

The average sample size was no more than 20 participants. The results for the scenarios of narrow safety window and all high show how the EWOC principle limits the risk of exposing participants from a toxic dose level. Overall, the scenarios illustrated above demonstrate that the model performs well in the hypothetical scenarios investigated by correctly identifying the MTD at least 62% of the time while limiting participants from receiving excessive/unacceptable toxic dose levels.

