5.1.2.1 Part 1: Dose Escalation

Six disease-restricted populations will be included in the dose-escalation part. These are melanoma, NSCLC, SCCHN, RCC, BUC, and gastric cancer. The dose-escalation part of the study will evaluate doses of BMS-986242 in combination with nivolumab based on DLTs using a BLRM model (for BMS-986242 monotherapy lead-in) and BLRM-copula model (for BMS-986242 in combination with nivolumab). The Bayesian models will be used for recommendation of the next dose to be investigated. BLRM (combined with copula) framework with an escalation with overdose control principle will be employed to ensure that safety is not compromised during dose escalation.

The initial dose level of BMS-986242 will be 12.5 mg administered orally daily. After a 2-week period, once initial lead-in monotherapy (Cycle 0) is deemed tolerable, combination with 480 mg flat dose nivolumab (Cycle 1) will be initiated.

Dose levels to be considered for the next combination cohort (with monotherapy lead-in) will be based on recommended monotherapy dose from BLRM and recommended combination dose from BLRM-copula. The lower dose from these 2 recommendations will be considered. Potential dose levels for dose escalation are provided in [Table 5.1.2.1-1](#). The maximum allowable increase in dose will be 100%. Final dose selection for the next cohort/dose level will be made in conjunction with all data available from PK and pharmacodynamic assessments, and will be made after discussion and agreement between investigators and BMS Medical Monitor. Accordingly, intermediate or lower doses, or less frequent dosing of BMS-986242 may be tested if none of the planned doses/schedules are found to be tolerated as the lead-in phase or in combination with nivolumab.

Initially, approximately 4 participants will be treated at the starting dose level of BMS-986242. During the dose-escalation phase, once a dose level has been decided, a set of approximately 4 participants will be initially treated at that specified dose level. Increments of approximately 3 participants will be added to each dose level depending on model recommendation and clinical judgment. Due to the potential for early discontinuation, additional participant(s) may be enrolled to ensure at least 3 evaluable participants at each dose level.

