10 STATISTICAL CONSIDERATIONS

10.1 Sample Size Determination

10.1.1 Dose Escalation

During the dose-escalation trial, the sample size at each dose in these arms depends on observed toxicity and posterior inference.

Up to approximately 78 participants are planned to be enrolled for Part 1 (dose escalation) and clinical pharmacology substudy: approximately 30 participants for the dose-escalation phase, with up to 24 additional participants in Part 1 for additional characterization of the safety, PK, and pharmacodynamic profile of BMS-986242, and approximately 24 participants for the clinical pharmacology substudy (including food effect). [Appendix 7](#) provides additional details for the operating characteristics of the BLRM for monotherapy and BLRM-copula for combination therapy based on doses from 25 mg; an addition of 12.5 mg is expected to provide similar operating characteristics..

For the food effect assessment, the sample size is not based on statistical power for comparison but on consideration of the precision of the estimates of geometric means of C_{max} and AUC(0-T) of BMS-986242.

For a sample size of 6 participants, there is an 80% probability for the 90% confidence interval to be within 79.6% to 125.7% of the point estimate of the geometric mean for C_{max} and within 80.4% to 124.4% of the point estimate of the geometric mean for AUC(0-T). This calculation assumes that log(C_{max}) and log(AUC[0-T]) of BMS-986242 are normally distributed with a standard deviation (SD) of 0.23 and 0.22, respectively, as estimated from a study of a related compound.

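### Table 4 simulates a lead-in escalation that skips dose levels, which the 100% limit forbids; under the written rules its average N is about 27, not at most 20, in two of three scenarios

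*Combined protocol and SAP*

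**What the plan says.** Protocol Section 5.1.2.1 sets the escalation rules. The planned levels (Table 5.1.2.1-1) are 12.5, 25, 50, 100, 200, 400 and 600 mg, and "The maximum allowable increase in dose will be 100" percent. Each level starts with about 4 participants, further participants are added in increments of about 3, and "additional participant(s) may be enrolled to ensure at least 3 evaluable participants at each dose level". The next dose comes from the monotherapy and the combination models together: "The lower dose from these 2 recommendations will be considered".

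Appendix 7, Section 3.1 describes the simulations: "The provisional dose levels for BMS-986242 monotherapy are 25 mg through 600 mg"; a fixed cohort size of 3; "Minimum number of participants treated at a given dose level in order to declare MTD: 6"; at most 12 at one dose; and "Maximum number of participants treated: 30". The list contains no limit on the size of a dose increase. From Table 4, Section 3.2.1 concludes that "The average sample size was no more than 20 participants" and that the MTD is correctly identified at least 62% of the time.

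Section 10.1.1 sends the reader to Appendix 7 for operating characteristics "based on doses from 25 mg; an addition of 12.5 mg is expected to provide similar operating characteristics".

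**The concern.** Every planned step from 12.5 to 400 mg is exactly +100%, and going from 200 straight to 600 mg would be +200%. Under the written limit a trial must therefore treat participants at every level below the dose it selects. Table 4's counts by dose do not look like that: almost nobody is treated at 50 mg, although almost every trial ends far above it.

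If Table 4 was run without the limit, its average sample size and correct-selection rate describe an escalation the protocol does not allow. A reader of Section 10.1.1 would take the lead-in model to need about 10 fewer participants on average than the approximately 30 planned. The statement that adding 12.5 mg changes little would also rest on skipping, because under the limit 12.5 mg is one more cohort that no trial can bypass.

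**Working it through.** **1. Are the printed counts averages over all trials?** The note to Table 4 mentions an adjustment for skipped dose levels, so this needs checking. The counts by dose sum to the printed average N:
- By Prior: 3.1 + 0.2 + 0.8 + 4.2 + 6.6 + 3.5 = 18.4
- Narrow Safety Window: 3.1 + 0.2 + 0.9 + 4.7 + 7.3 + 2.1 = 18.3
- All High: 4.6 + 1.5 + 0.7 + 0.3 + 0.6 + 0 = 7.7

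They are plain averages over all trials.

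**2. Do they show skipping?** Share of trials selecting 200 mg or more:
- By Prior: 25.9 + 46.5 + 24.7 = 97.1%
- Narrow: 29.7 + 62.9 + 4.8 = 97.4%

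Under the limit each of these trials treats at least one cohort of 3 at 50 mg and at 100 mg, so each mean must be at least 0.971 × 3 = 2.9 (Narrow: 0.974 × 3 = 2.9). The printed means are 0.2 at 50 mg and 0.8 / 0.9 at 100 mg. At most 0.2/3 = 6.7% of trials treated anyone at 50 mg, and at most 27% to 30% at 100 mg. The counts are impossible under the written limit. Table 5 does not show this (3.2 participants at 50 mg in every scenario).

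**3. Size by hand from Table 4.** Raise 50 and 100 mg to 2.9 and leave 200 to 600 mg as printed:
- By Prior: 18.4 + 2.7 + 2.1 = 23.2; with a 12.5 mg cohort of 3, 26.2
- Narrow: 18.3 + 2.7 + 2.0 = 23.0; with 12.5 mg, 26.0

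The shortest possible path gives a floor: from 12.5 mg, 3 at each lower level and exactly 6 at the selected dose, so N = 15, 18, 21 and 24 for 100, 200, 400 and 600 mg (9 and 12 for 25 and 50 mg). Use the printed selection shares and count the 0.2% / 0.4% of trials that select no dose at 3 each:
- By Prior: 0.026×15 + 0.259×18 + 0.465×21 + 0.247×24 + 0.002×3 = 20.8
- Narrow: 0.002×9 + 0.003×12 + 0.017×15 + 0.297×18 + 0.629×21 + 0.048×24 + 0.004×3 = 20.0

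**4. Re-simulation.** Inputs from Appendix 7: the Table 1 prior with reference dose 600 mg; overdose probability below 25%; next dose maximises the probability of a 16% to 33% DLT rate; stop at 6 or more at a dose with target probability above 50%, at 12 at a dose, or at N = 30; true rates from Table 4. Assumed: a true rate of 1% at 12.5 mg. The ranges are over separate runs with 1,500 to 10,000 trials per design where the number was recorded.

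| Design (cohorts of 3) | By Prior | Narrow |
|---|---|---|
| Printed | 18.4 | 18.3 |
| As simulated, no limit, 25 mg start | 19.2–19.9 | 19.9–20.1 |
| 12.5 mg start only | 19.8–20.6 | 20.0–20.2 |
| 100% limit only | 24.4–24.5 | 24.2–24.4 |
| Both | 26.7–26.9 | 26.7–26.9 |

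The unmodified runs come within 2 participants of the printed figures, with similar counts by dose (By Prior 3.2 / 0.1 / 1.1 / 4.5 / 6.7 / 4.2 in one run). At least 97% of those trials skip a level.

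Sensitivity with both changes:
- True rate at 12.5 mg from 0 to 2%: 26.6 to 26.9.
- Stop at 9 instead of 12 at a dose: 25.3 to 25.6.
- No maximum of 30: 27.5 / 27.3.
- First cohorts of 4, then 3: 28.7–29.0 / 28.8–28.9.
- All High: 8.7, assuming a 30% rate at 12.5 mg.

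**5. The whole trial.** With the lower-of-two rule in the Additive scenario, average N is 19.2 to 21.2 with cohorts of 3, and 24.4 to 25.3 with 4 then 3. This uses 600 trials per setting. It assumes a gamma shape of 13.5 for the interaction parameter, nivolumab 480 mg equal to 1 or 2 times its reference dose, and an 11% combination DLT rate at 12.5 mg.

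**The case against.** The quoted sentence truthfully reports the simulation that was run: 18.4, 18.3 and 7.7 are all below 20. That stands, and the fault is a mismatch between the simulated and written designs, not a wrong sum.

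The trial never escalates on the monotherapy model alone. Under the lower-of-two rule with cohorts of 3, the average is again near 20. This also stands, and it is why the planned number is not challenged. But Section 10.1.1 cites Appendix 7 for the monotherapy model separately, and Table 4 does not model the lower-of-two rule either.

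The uncapped behaviour is visible: the Table 4 note mentions skipped levels, and Appendix 7, Section 4 shows a model recommendation of 400 mg after 25 mg. Section 10.1.1 discloses the 25 mg start and Section 3.1 the cohorts of 3. Yet no sentence says that the 100% limit was left out.

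Precision is limited. The strict floor from Table 4 is only 20.8 and 20.0, and 17.8 and 17.0 without the 12.5 mg cohort, so the figures in the mid-20s need simulation or the printed counts at 200 to 600 mg held fixed. The stopping logic is not fully specified. The share of trials reaching 30 is 38% to 43% under the stated rules, but 24% / 18% if trials stop at 9 at a dose. All the same, every variant near the printed figures puts the average at 25 or more.

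**Conclusion.** The concern holds. Table 4 was produced without the 100% limit in Section 5.1.2.1; this follows from its printed counts and needs no simulation. Under the written limit and the 12.5 mg start, the lead-in model's average N in the By Prior and Narrow scenarios is about 27 with cohorts of 3 (25 to 27 across stopping variants), against the printed 18.4 and 18.3. The limit accounts for most of the rise. Without it, adding 12.5 mg changes the average by less than 1 participant; with it, by more than 2. The statement about similar operating characteristics therefore does not carry over to the written design.

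Three things are not claimed:
- The planned figure of approximately 30 is not shown to be too small.
- The All High scenario is not affected in this way.
- No set loss of accuracy is asserted. Unmodified runs give 66% and 51% to 55% correct selection against the printed 71.2% (46.5 + 24.7) and 62.9%. Runs of the written design range over 36% to 64% and 31% to 53%, depending on cohort size and on how the MTD is chosen at N = 30, which is not stated. The figure of at least 62% is therefore unverified for the written design.

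**What to change.** Reconcile Table 4 with Section 5.1.2.1. Preferably, re-run Tables 4 and 5 on the 12.5 to 600 mg levels with the written limit on increases, with first cohorts of 3 and of 4 evaluable participants, and with the lower-of-two rule. State how the MTD is selected when the maximum N is reached. Then replace the average-sample-size sentence, the correct-identification figure and the similar-operating-characteristics sentence with the results: average N, correct selection, and share of trials reaching 30.

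At minimum, state in Section 10.1.1 and Appendix 7 that Table 4 omits the 100% limit and does not describe the written escalation.

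One editorial correction while editing: the lower end of the correct-identification range in Appendix 7, Section 3.2.2 should be 48%, not 49% (7.9 + 10.7 + 29.5 = 48.1).

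The cost is simulation time, or two sentences for the minimum. The restated monotherapy average will be higher than printed. The point asks for no change to the planned number, the dose levels or the escalation rules.

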3.2.2 Operating Characteristics of BLRM-copula for Combination Therapy

Three hypothetical scenarios were investigated: (1) additive joint toxicity; (2) toxicity rates 25% higher than the additive scenario; (3) toxicity rates 50% higher than the additive scenario (Table 5).

Table 5: Simulation Results of BLRM-Copula for Combination

Scenario	BMS-986242 Dose	25	50	100	200	400	600	MTD not selected (%)	Fitted MTD	Toxicity Observed (%)	Avg # Pts
Additive	% DLT	12	14	17 ^a	23 ^a	32 ^a	40				
	% MTD	2.7	5.7	23.6	24.6	23.6	9.8	10	464.7	24.3	19.5
	# Pts	3.6	3.2	4.7	3.6	2.4	2.2				
	#DLT	0.5	0.4	0.7	0.8	0.7	0.9				
25% Higher	% DLT	15	18 ^a	21 ^a	29 ^a	40	50				
	% MTD	5.5	8.7	26.4	29.8	12.9	2.6	14.1	357.2	27.7	17.7
	# Pts	3.8	3.2	4.5	3.5	1.7	1.1				
	#DLT	0.6	0.6	0.9	0.9	0.7	0.6				
50% Higher	% DLT	18 ^a	21 ^a	26 ^a	34	48	60				
	% MTD	7.9	10.7	29.5	24.5	5.4	0.2	21.8	291.7	31.7	15.5
	# Pts	3.9	3.2	4.1	2.8	0.9	0.6				
	#DLT	0.7	0.7	1.0	0.9	0.5	0.3				

^a Doses with true target toxicity within the target toxicity interval [16%, 33%]

Note: % DLT = true DLT rate; % MTD = proportion of the dose selected as the MTD; #DLT = average number of DLTs; MTD not selected = dose was below lowest dose or above highest dose; Fitted MTD = fitted MTD at 33% as the target toxicity rate; Toxicity observed = Average proportion of DLTs out of all simulated trials; # Pts = average number of participants

The average sample size was around 20 participants. The results show how the EWOC principle limits the risk of exposing participants from unacceptable toxic dose levels. Overall, the scenarios illustrated above demonstrate that the model performs well by correctly identifying the MTD ranging from 49% to 72% in the hypothetical scenarios investigated while limiting participants from receiving unacceptable toxic dose levels.

[figure not shown]
4 INTERIM MONITORING CASE STUDY TO ILLUSTRATE PROVISION OF DOSE RECOMMENDATIONS DURING DOSE ESCALATION

In order to provide a comprehensive view of the dynamics of the models, different hypothetical scenarios exploring different possibilities are examined. For the simplicity of illustration purposes, a static cohort size of 3 subjects is applied for dose level 25 mg. This cohort size could vary during the actual clinical trial, and the BLRM (-Copula) models are designed to fit various different cohort sizes, adaptively. In general, there are many possible scenarios for a specific dose level, especially with a monotherapy lead-in followed by combination treatment. For example, there could be 0, 1, 2, or 3 DLTs observed in the monotherapy lead-in period, and similarly 0, 1, 2, or 3 DLTs observed in the combination period.

During interim monitoring, posterior probabilities will be updated when there is new DLT information available. The following two visualization plots will be produced to reflect the real time dose-DLT relationship, to quantify benefit (in the form of target dosing) and risk (in the form of overdosing and underdosing) during the model’s recommendation process, and to facilitate clinical team’s interpretation of the model recommendations for the final decision making:

- Dose-DLT profile for the doses ranging between 0 mg and 600 mg (Figure 1).
- Stacking histograms displaying predictive probabilities on DLT rates classified into 3 different categories (Underdosing, Target Dosing and Overdosing) (Figure 2).

Figure 1: An Example of Updated Dose-DLT Profile After Incorporating Prior Information and DLT Information at 25 mg (0/3 DLTs in Monotherapy Lead-in and 0/3 DLTs in Combination at 25 mg for BMS-986242)

Interpretation and usage of Figure 1:

Figure 1 is a snapshot of an updated dose-DLT profile with DLT information available at dose level 25 mg after the combination period (assuming there was no DLT in either monotherapy lead-in or combination period). The dose-DLT profile is captured with a continuous dose spectrum ranging from 0 mg through 600 mg, which is a slice of the dose-DLT surface of the combination of two drugs with nivolumab fixed at 480 mg. For each dose within the range, there is a corresponding distribution of the predicted DLT rates calculated from the posterior samples of the

[figure not shown]
model parameters. This figure will be updated each time new DLT information becomes available from different dose levels.

In [Figure 1](#), there are 3 different quantiles (2.5%, 50%, and 97.5%) plotted to characterize the current trend of the toxicity profile (as shown by the 50% quantile), as well as the variation of the dose-DLT profile (as shown by the 2.5% quantile and the 97.5% quantile), according to the accumulation of DLT data from all previous and current dose levels. The toxicity boundaries (0.16 and 0.33) are illustrated in two horizontal lines to benchmark the way in which the dose-DLT profile is trending.

Intermediate dose levels can be identified using different boundary cutoffs. For example, using the 50% quantile curve (green highlight), which represents the nearly average DLT distribution for each dose level, 350 mg could be a potential intermediate dose level corresponding to the lower pre-specified DLT rate boundary of 0.16, and 600 mg could be a fitted MTD dose level associated with the upper boundary of 0.33.

Moreover, if all of the current pre-specified doses are considered intolerable (overdosing probabilities > 0.35 for combination therapy, for example, a case not shown on the current [Figure 1](#)), the model will recommend to stop the current dose level, and the clinical team can leverage the current updated dose-DLT curve to pinpoint a new dose, which is lower than pre-specified lowest dose (25 mg) by using the DLT rate boundaries.

Figure 2: An Example of Updated Stacking Histogram After Incorporating Prior Information and DLT Information at 25mg (0/3 DLTs at Monotherapy Lead-in and 0/3 DLTs at Combination) to Classify Predicted DLT Rates into 3 Categories (Underdosing, Target Dosing, and Overdosing)

Interpretation and usage of Figure 2:

Figure 2 is a snapshot of stacking histogram with DLT information available at dose level 25 mg after combination period (assuming there was no DLT in either monotherapy lead-in or combination period). This figure will be updated each time new DLT information becomes available in different dose levels.

When recommending the next dose level, the model will first exclude doses that are intolerable (with overdosing probabilities $\geq 35\%$ or $\geq 25\%$ for combination and monotherapy respectively). Among those qualified candidate doses that are considered “tolerable”, the model will select the dose that maximizes the probability of being within the target toxicity range (DLT rate of 16% up to 33%).

As illustrated in Figure 2, when there is 0 DLT observed out of 3 subjects for the dose level 25 mg in both monotherapy lead-in and combination, the distribution of predicted DLT rates will be characterized into possibilities falling into 3 different categories. Some dose levels for BMS-986242 might be excluded according to the higher-than-cutoff overdosing probabilities (eg, 600mg, $> 35\%$). Among the remainder of tolerable dose levels, the BLRM (-Copula) model recommends the dose that maximizes the probability of being within the target dosing interval.

[figure not shown]
Therefore, the model's recommendation would be to escalate to 400 mg, which is associated with the highest target dosing probability of 27% compared with that of other dose levels.

Similarly (although not shown on Figure 2), according to the rules specified above, the model could possibly recommend to de-escalate to a lower dose level than current treated dose level, extend the current dose level, or even to stop and identify a new dose level lower than 25 mg, the lowest pre-specified dose level. Please refer to description of Figure 1 for details on how to specify the new dose levels.

